10.4 Statistical Analyses

The statistical analysis plan will be developed and finalized before database lock and will describe the patient populations to be included in the analyses, and procedures for accounting for missing, unused and spurious data.

The statistical analysis plan will specify how lost to follow-up patients will be addressed in the primary analysis.

10.4.1 *General Methods*

All summarizations will be presented separately for each cohort, and over all subjects combined.

For continuous variables, descriptive statistics (number (n), mean, median, standard deviation, minimum and maximum) will be presented. For categorical variables, frequencies and percentages will be presented. For time-to-event variables, percentages of patients experiencing that event will be presented and median time-to-event will be estimated using the Kaplan-Meier method. As appropriate, a 95% CI will be presented. Graphical displays will be presented, as appropriate.

Patients demographic characteristics including age, gender, and race will be analyzed, with categorical variables summarized in frequency tables while continuous variables summarized using mean (standard deviation) and median (range).

All data collected will be presented in by-patient data listings.

10.4.2 *Efficacy Analyses*

ORR is defined as the proportion of patients with a confirmed best response of iCR or iPR by iRECIST. Objective response rate will be estimated, and 90% CI based on the exact binomial distribution will be presented by cohort and overall, including number and percent of patients in each overall response category.

The primary analysis will be based on objective response at Week 12. An additional analysis of ORR based on best objective response during the study will be performed.

DOR, DCR, PFS, and OS will also be calculated, defined as follows:

- DOR: time from date of first response to date of progression, where patients without progression are censored at date of last valid disease assessment
- DCR: proportion of patients with SD or better (PR and CR). SD for at least six months
- PFS: time from date of start of treatment to date of progression, where patients without progression are censored at date of last valid disease assessment
- OS: time from date of start of treatment to date of death or censored at date of last contact

Efficacy analyses will be performed using the efficacy-evaluable analysis set.

10.4.3 *Safety Analyses*

Safety evaluations will be based on the incidence, severity, attribution and type of AEs, and changes in the patient's vital signs, and clinical laboratory results, analyzed using the safety analysis set.

Summarization of toxicity data will focus on incidence of treatment-emergent adverse events. Treatment-emergent adverse events are defined as any AE that occurs during or after administration of the first dose of treatment through 30 days after the last dose, any event that is considered study drug-related regardless of the start date of the event, or any event that is present at baseline but worsens in intensity. The incidence of serious adverse events, adverse events, drug-related adverse events, and adverse events leading to discontinuation or death will be presented in tabular form by system organ class and preferred term. Adverse events will be assessed for severity according to the NCI CTCAE, version 5.0.

A presentation of dose-limiting toxicities among patients in the safety run-in set will be presented.

Other safety evaluations including vital sign, laboratory and physical exam results will be presented over time.

10.4.4 *Other Analyses*

Antigen-specific cellular immune response assessed by but not limited to Interferon- γ secreting T lymphocytes will be summarized by visit. Immune related gene expression will be evaluated with pre- and post-treatment tissue biopsies. Cytokine and chemokine profiles will be summarized by visit.

Additional exploratory analyses may be performed, including evaluation of relationship between efficacy endpoints and immunology parameters.

10.4.4.1 *Pharmacodynamics*

Exploratory pharmacodynamic (PD) analysis will be performed using dose, vaccine-specific antibody response (geometric mean titer), antigen-specific T and B cell indices, and the relative expression of ASPH in each patient's tumor. The PD will be balanced and optimized to the degree of antigen-specific immune response and minimized for the production of regulatory immune processes.

10.5 *Interim Analyses*

For each cohort, the objective response rate will be assessed at the completion of stage 1 of the 2-stage design, after 15 patients complete the 12-week follow-up period or discontinue prior due to disease progression. See Section 10.2 for additional details.

10.5.1 *Safety Committee*

To ensure patient safety during the study, a Safety Committee will be formed to monitor safety on a periodic basis. Members of the Safety Committee will include a Safety representative, Principal Investigator(s) and the Sponsor Medical Expert. A charter will outline their roles and responsibilities. The Safety Committee will meet at the completion of the safety run-in to review safety data collected from the point of first patient in (FPI) to review safety, or as needed. The safety data will include demographic data, adverse events, serious adverse events, and relevant laboratory data. Following each data review, the Safety Committee will provide recommendations as to whether the study should continue or be amended, or whether the study should be stopped on the basis of safety (i.e., evidence of harm). The final decision will rest with the Sponsor. For each cohort, the interim efficacy assessment will occur after 15 patients were enrolled and completed the 12-week follow-up period. A safety review will occur in parallel to the efficacy assessment of the first 15 patients in each cohort. Any outcomes of these safety reviews that affect study conduct will be communicated in a timely manner to the investigators for notification of the Institutional Review boards/Ethics Committees (IRBs/ECs).

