9.1 Efficacy Assessments

9.1.1 *Tumor Assessment*

Initial (screening) tumor assessments must be performed within 28 days prior to the first dose of study treatment. The investigator/site radiologist must review pre-trial images to confirm the patient has measurable disease per RECIST 1.1 ([Appendix B: Tumor Assessment Criteria](#)). Tumor assessments performed as standard of care prior to obtaining informed consent and within 28 days of the first dose of study treatment may be used rather than repeating tests. Beginning with screening, all imaging assessments will be evaluated using RECIST 1.1. On-study imaging assessments will be performed every 6 weeks (Q6W) calculated from the date of therapy initiation and independent of treatment delays. RECIST 1.1 will be used by the site for treatment decisions until the first radiologic evidence of progressive disease (PD). The Sponsor may request digitized scans from patients to confirm response.

Following the first radiologic evidence of PD by RECIST 1.1, treatment decisions may be made by using immune iRECIST ([Appendix B: Tumor Assessment Criteria](#)) to accommodate tumor response patterns seen with CPI therapy including pembrolizumab treatment (e.g., tumor flare). This was described by Nishino, et al. 2016 [\[13\]](#) and is used in immunotherapy clinical trials. For a clinically stable subject with first radiologic evidence of PD, it is at the discretion of the site investigator to continue treating the subject with SNS-301 and pembrolizumab until PD is confirmed at least 4 weeks after the date of the first tumor imaging suggesting PD per the site investigator. If radiologic PD is confirmed by the subsequent tumor imaging, the subject should be discontinued from treatment unless, in the opinion of the investigator, the subject is achieving a clinically meaningful benefit. In this case, an exception for continued treatment may be considered following consultation with the Sponsor. Additional treatment response evaluation by RECIST v 1.1 and iRECIST may be performed at the Sponsor's discretion.

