Patients will undergo tumor assessments every 6 weeks (± 7 days) until approximately 12 months following first dose of study treatment, or earlier if clinically indicated. After 12 months, tumor assessments will be required every 12 weeks (± 7 days). Imaging should continue to be performed until disease progression is assessed by the Investigator, the start of new anti-cancer treatment, withdrawal of consent, death or the end of the trial, whichever occurs first for efficacy follow-up. Patients who start a new anti-cancer therapy will be censored for survival and progression analyses at date of last scan prior to the start of new anti-cancer therapy.

Tumor imaging should be performed by computed tomography (CT), but may be performed by magnetic resonance imaging (MRI) if CT is contraindicated, but the same imaging technique should be used in patient throughout the trial. CT scans (with oral/IV contrast unless contraindicated) must include chest, abdomen and pelvis. The investigator must review before dosing at the next visit. Per RECIST 1.1, response should be confirmed by a repeat radiographic assessment. The scan for confirmation of response may be performed no

earlier than 4 weeks after the first indication of response, or at the next scheduled scan, whichever is clinically indicated.

Patients who have unconfirmed disease progression may continue on treatment until progression is confirmed. If radiologic imaging by local/site assessment shows progressive disease (PD), tumor assessment may be repeated 4 weeks later in order to confirm PD with the option of continuing treatment per below while awaiting radiologic confirmation of progression. If repeat imaging shows SD, PR or CR, treatment may be continued as per treatment schedule. If repeat imaging still meets the threshold for PD ($\geq 20\%$ increase in tumor burden compared to nadir) but shows a reduction in tumor burden compared to the previous time point, treatment may be continued as per treatment calendar after consultation with Sponsor. If repeat imaging confirms progressive disease without reduction in tumor burden compared to the previous time point, patients will be discontinued from study treatment.

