Version 1.0

Sponsor: Sensi Biotherapeutics

Protocol: SNS301-2-2

This study will employ a Simon 2-stage design, with 15 evaluable patients (i.e. meeting the definition for the efficacy evaluable analysis set; at Week 12 for both cohorts. Non-evaluable patients will be replaced.

The safety run-in will be performed using a modified rolling six design which will enroll up to six patients (safety analysis patients). These patients may contribute to the first 15 in stage 1, assuming they meet the definition for evaluable for efficacy. The end of the safety run-in period is defined as the earliest of the following:

- The first three patients have all completed Week 6 with no DLTs experienced by any of the safety runin patients in that cohort (up to six); enrollment may then proceed through stage 1;
- All six patients of the safety run-in phase, have completed week six with only one patient having experienced a DLT; enrollment may then proceed through stage 1;
- Two or more of the safety run-in patients, have experienced DLTs prior to completing Week 6; enrollment will be suspended.

If at least one responder (ORR per iRECIST) is observed in the first 15 evaluable patients (i.e. meeting the definition for the efficacy evaluable population) by Week 12, then the study will continue to Stage 2 and enroll up to 15 additional patients. If at least 4 responders are observed overall, further research will be deemed warranted.

[figure not shown]
There will be a waiting period of one week between enrollment of the first patient and the second patient because this trial is treating patients with SNS-301 and pembrolizumab for the first time. The interim efficacy assessment, for each cohort, will occur after 15 patients were enrolled and completed the 12-week follow-up period. A safety review will occur in parallel to the efficacy assessment of the first 15 patients

The trial will be stopped if any adverse experience of any related death, grade 4 autoimmune toxicity or any grade 4 toxicity that is considered to have a causal relationship to study drug should occur. These events will be submitted to regulatory agencies within the expedited safety reporting criteria.

The clinical trial will be considered completed when all patients have had their three-year follow-up visit, death, lost to follow-up, withdrawal of consent, or when the Sponsor deems the study completed, whichever comes first.

The study schema is presented in Figure 1:

Figure 1: Study Schema

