# 7. EFFICACY ANALYSIS

## 7.1 Primary Efficacy Analysis

The primary efficacy analysis will be based on the Efficacy-Evaluable Analysis Set at week 12. All efficacy variables will be presented by cohort. The following primary efficacy variables will be summarized to determine the anti-tumor activity of SNS-301:

Objective Response Rate (ORR)

- ORR is defined as the proportion of patients with a confirmed best response of iCR or iPR by iRECIST.
- ORR, and 90% CI at week 12 based on the exact binomial distribution will be presented, including number and percent of patients in each overall response category.

Sponsor: Sensi Biotherapeutics

Protocol: SNS301-2-2

- Best Overall Response ( BOR) will also be presented.

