## 9.5 Interim Analysis and Data Monitoring

A Safety Committee will be formed to monitor safety on a periodic basis. The Safety Committee will meet at the completion of the safety run-in to review safety data collected from the point of first patient in (FPI) to review safety, or as needed. The safety data will include demographic data, adverse events, serious adverse events, and relevant laboratory data.

The interim efficacy assessment, for each cohort, will occur after 15 patients were enrolled and completed the 12-week follow-up period. The objective response rate, for each cohort, will be assessed at the completion of stage 1 of the 2-stage design, after 15 patients complete the 12-week follow-up period or discontinue prior due to disease progression. A safety review will occur in parallel to the efficacy assessment of the first 15 patients in each cohort.

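### A response first seen at Week 12 cannot be confirmed before about Week 16–18, but the confirmed-response stage 1 look is set at 12 weeks and the plan does not settle how to count it

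*Protocol*

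**What the plan says.** **Endpoint.** SAP 7.1 states that "ORR is defined as the proportion of patients with a confirmed best response of iCR or iPR by iRECIST"; protocol 10.4.2 gives the same definition. On timing, protocol 10.4.2 says: "The primary analysis will be based on objective response at Week 12". It then adds a separate analysis of best response over the whole study.

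**Scans and confirmation.** Protocol 9.1.1: "On-study imaging assessments will be performed every 6 weeks (Q6W) calculated from the date of therapy initiation". It continues: "Per RECIST 1.1, response should be confirmed by a repeat radiographic assessment". The confirming scan may come no "earlier than 4 weeks after the first indication of response, or at the next scheduled scan".

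**Stage 1 look.** Protocol 10.5 places it "after 15 patients complete the 12-week follow-up period or discontinue prior due to disease progression". SAP 9.5: "The interim efficacy assessment, for each cohort, will occur after 15 patients were enrolled and completed the 12-week follow-up period". SAP 2.2 applies the one-responder rule to responders observed "by Week 12, then the study will continue to Stage 2 and enroll up to 15 additional patients". The DOR bullets in SAP 7.1 report median duration for patients whose CR or PR is confirmed as of 12 weeks.

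**Best-response tables.** The iRECIST part of protocol Appendix A says that every patient's best response is classified by its Table 2, and the note to that table assumes that CR and PR need no confirmation. SAP Appendix F does require confirmation, but has no rows for unconfirmed or confirmed immune progression (iUPD, iCPD).

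**The concern.** The endpoint requires confirmation, yet the time at which it is counted leaves no room to confirm a response first seen on the Week 12 scan. The two best-response tables then pull in opposite directions. Two analysts with the same data could report different stage 1 counts: one scores a Week 12 response as a failure, one holds it, and one who follows iRECIST Table 2 counts it without confirmation.

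The thresholds are small: at least 1 response in 15 for Cohort A and at least 2 in 15 for Cohort B (protocol 10.2). A single pending response can therefore be the difference between meeting and missing the continuation rule. Because the trial is open-label, a counting rule settled at the look would be settled with the responses in view.

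**Working it through.** **1. Timing (protocol 9.1.1).** Scheduled scans: Weeks 6, 12, 18.
- First seen at Week 6: earliest confirmation 6 + 4 = Week 10; the Week 12 scan serves.
- First seen at Week 12: earliest confirmation 12 + 4 = Week 16; next scheduled scan 12 + 6 = Week 18. With the ±7-day window, about Week 15 (11 + 4) to Week 19 (18 + 1).

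On the scheduled scans, only a Week 6 response can be confirmed by Week 12.

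**2. The readings side by side.**
- *Strict.* SAP 2.2 (by Week 12) together with the DOR bullet in SAP 7.1 suggests that confirmation must be complete at Week 12. Later responses enter only the additional best-response analysis in protocol 10.4.2.
- *Pending.* A response first seen by Week 12 may be confirmed later. No text then says how it is handled at the look.
- *No confirmation.* iRECIST Table 2, taken at its word, contradicts protocol 10.4.2 and SAP 7.1.

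SAP Appendix F serves patients without pseudoprogression, because a footnote to iRECIST Table 1 says the CR, PR and SD categories are then the same. It does not classify a response after iUPD, which Appendix A allows. The 4-week interval is itself introduced as a RECIST 1.1 rule; no separate interval is given for confirming an iRECIST response.

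**3. The plan's own figures (protocol 10.2).** With X1 and X2 each Binomial(15, p), stage 1 threshold r1 and final threshold r:
- P(stop) = P(X1 < r1)
- P(reject) = Σ over x ≥ r1 of P(X1 = x) · P(X2 ≥ r − x)

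| | A: r1 = 1, r = 4, 5% v 18% | B: r1 = 2, r = 7, 13.3% v 29% |
|---|---|---|
| Power (stated) | 0.8002 (80%) | 0.8006 (80.1%) |
| Type I error (stated) | 0.0582 (6%) | 0.0917 (9.2%) |
| Stop under null (stated) | 0.95^15 = 0.4633 (46%) | 0.3881 (38.8%) |
| False stop under alternative | 0.82^15 = 0.0510 | 0.71^15 + 15 × 0.29 × 0.71^14 = 0.0419 |

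Every stated figure reproduces.

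**4. Size of a stage 1 miscount.** Let k of the 15 patients lack a Week 18 scan at the look, and let a share L of their responses be first seen at Week 12 and scored as non-response. Neither value is in the documents.
- *k.* 30 patients per cohort over the stated 18–24 months is 1.25–1.67 per month, or 1.7–2.3 in 6 weeks, giving k = 2–3. Protocol 3.1.2 reports 11 enrolled at 29 October 2020, and Appendix C records 9 at 23 July 2020: 2 patients in 98 days, one per 7 weeks, giving k = 1. Range used: 1–3.
- *L.* Assumed 10–50%.

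A late patient is seen as a responder with probability p(1 − L).
- A: false stop = 0.82^(15−k) × [1 − 0.18(1 − L)]^k. For k = 1, L = 10%: 0.82^14 × 0.838 = 0.0521. For k = 3, L = 50%: 0.82^12 × 0.91^3 = 0.0696.
- B: false stop = P(Bin(15−k, 0.29) + Bin(k, 0.29(1 − L)) ≤ 1), which gives 0.0432 and 0.0657.

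With all confirmed responses counted at the final read:

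| | Plan | k = 1, L = 10% | k = 3, L = 50% |
|---|---|---|---|
| A false stop | 0.0510 | 0.0521 | 0.0696 |
| A power | 0.8002 | 0.7996 | 0.7899 |
| A type I error | 0.0582 | 0.0582 | 0.0567 |
| B false stop | 0.0419 | 0.0432 | 0.0657 |
| B power | 0.8006 | 0.7999 | 0.7889 |
| B type I error | 0.0917 | 0.0915 | 0.0889 |

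The rise in stopping is the chance that a pending response which later confirms decides stage 1. Under the alternative it is 0.0011–0.0187 (A) and 0.0014–0.0239 (B); under the null, 0.0024–0.0375 (A) and 0.0039–0.0602 (B).

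**The case against.** The best defence is that the plan is strict rather than silent. SAP 2.2 and the DOR bullet both treat confirmed status as something held at 12 weeks, the hypotheses in protocol 10.2 are framed as response rates at 12 weeks, and later responses go to the additional best-response analysis. This reading is coherent, and a plain statement of it would also remove the ambiguity. What stands against it is that the protocol's primary-analysis sentence does not say it, its main support is a bullet on another endpoint, and iRECIST Table 2 says something different again.

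Second, stopping is not automatic. The documents say when a cohort continues; the Cohort B wording is permissive, and nothing forbids waiting six weeks for a scan that is already scheduled. That is right: a wait is allowed. But it is not required, so the outcome rests on a choice made at the look.

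Third, recent accrual points to k = 1, and L has no source. Both are fair, which is why the effect is given as a range that starts almost at the planned values.

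Fourth, the note to Table 2 reads as a carry-over from the published guideline, and the trial's own definition should prevail. Probably so, but Appendix A applies that table to all patients without excepting the note, and the SAP table that requires confirmation leaves out response after iUPD.

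**Conclusion.** The point holds. The confirmed-response definition, the 6-week scans, the confirmation interval and the 12-week look do not fit together for a response first seen at Week 12, and the best-response tables do not resolve it. The plan should settle this before a stage 1 decision depends on it.

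The shown effect is small. With 1–3 late patients and 10–50% of their responses first seen at Week 12, false stopping moves from 5.1% to 5.2–7.0% (A) and from 4.2% to 4.3–6.6% (B). Power stays at about 79–80% when the final read includes all confirmatory scans, and type I error does not exceed plan.

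Three stronger conclusions that a reader might draw are not supported:
- *That the printed operating characteristics are wrong or power collapses.* Losing 10–50% of all responses at both stages would give power of 72–27% (A) and 69–13% (B), but only if 18% and 29% are not rates of the endpoint as strictly counted. The documents label them as 12-week rates and give no time-to-response data.
- *That the final read would also miss confirmations.* Follow-up runs up to three years (protocol 5.3), and the SAP ties its outputs to the study report and final database lock (SAP 1 and 10).
- *That a pending response forces a cohort to close.* No text makes stopping mandatory.

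**What to change.** - In protocol 10.4.2 and 10.5 and SAP 2.2, 7.1 and 9.5, define a primary responder as a patient with iCR or iPR first documented at or before the Week 12 scan and confirmed at least 4 weeks later; the scheduled Week 18 scan suffices. Align the DOR bullet in SAP 7.1 with this.
- State that stage 1 futility is not declared while a pending Week 12 response that could change the decision awaits its confirmatory scan. No wait is needed if confirmed responses already meet the threshold, or if the pending ones could not reach it.
- State that the no-confirmation note to iRECIST Table 2 does not apply to the primary endpoint, and place beside SAP Appendix F a confirmed best-response rule that covers response after iUPD.

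Cost: wording in both documents, and a delay of about 6 weeks plus the 7-day window only when a pending response is decisive. Under the assumptions above, responses that later confirm would cause such a wait in at most about 2.4% of trials under the alternative and 6.0% under the null; responses that fail to confirm would add some. No extra scans are needed, because Week 18 imaging is already scheduled.

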9.2.14.6 Follow-Up

Survival follow-up information will be collected via telephone calls, patient medical records, and/or clinical visits approximately every 3 months for up to 3 years, until death, lost to follow-up, withdrawal of consent, or trial termination by Sponsor. All patients will be followed for survival and new anticancer therapy information unless the patient requests to be withdrawn from follow-up; this request must be documented in the source documents

and signed by the investigator. If the patient discontinues study treatment without documented clinical disease progression, every effort should be made to follow up regarding survival, progression (if not already progressed), and new anti-cancer therapy.

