### *Efficacy-Evaluable Analysis Set*

The Efficacy-Evaluable Analysis Set comprises all patients who receive at least 1 dose of the study treatment or component of the study treatment and have a post baseline response assessment per iRECIST at Week 12. Subjects who discontinued prior to Week 12 due to radiological disease progression will be included. Subjects who do not have a post baseline response assessment conducted will not be included in the analysis of efficacy.

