#### Overall Survival (OS)

- OS is defined as time from date of start of treatment to date of death.
- OS rate at 12 weeks and the corresponding 95% CIs will be calculated and summarized based on Kaplan-Meier product limit estimates and will be displayed along with the corresponding number of subjects at risk.
- Subjects who are still alive will be censored on the date of last contact.
- The 25th percentile, Median, and 75th percentile of OS as well as the corresponding 95% confidence limits will be estimated using Kaplan-Meier method. Number of patients who died and number censored will be presented.
- Kaplan-Meier curves of OS by cohort will be displayed graphically.

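### OS runs from first dose but is analysed only in patients with a Week 12 assessment or earlier progression, so some early deaths drop out; the rules for who counts also conflict

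*Protocol*

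**What the plan says.** Protocol 10.4.2 defines "OS: time from date of start of treatment to date of death or censored at date of last contact" and closes the section with "Efficacy analyses will be performed using the efficacy-evaluable analysis set". SAP 7.1 opens with "The primary efficacy analysis will be based on the Efficacy-Evaluable Analysis Set at week 12", lists OS among the variables that follow, and adds that "OS rate at 12 weeks and the corresponding 95% CIs will be calculated and summarized based on Kaplan-Meier product limit estimates". Protocol 4.2.1 places OS among the primary endpoints. No OS or ORR analysis in all treated patients is specified.

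The efficacy-evaluable set (Protocol 10.3, SAP 4) requires one dose and an iRECIST assessment at Week 12, with an exception for patients who stop earlier because of progression. Survival data are collected regardless of membership: "All patients will be followed for survival and new anticancer therapy information unless the patient requests to be withdrawn from follow-up" (Protocol 9.2.14.6).

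The surrounding rules do not agree:

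- **Early-progression exception.** The synopsis does not say what kind of progression counts. Protocol 10.3 says clinical progression. SAP 4 says "Subjects who discontinued prior to Week 12 due to radiological disease progression will be included". Protocol 10.3 also excludes anyone with no post-baseline assessment, directly after admitting clinical progressors.
- **Futility count, Cohort A.** SAP 2.4 leaves out patients who have progressed or are unevaluable at 12 weeks. The synopsis, Protocol 10.5 and SAP 9.5 count early progressors.
- **Replacement.** Protocol 5.2 and SAP 2.2 and 9.1 replace non-evaluable patients. Protocol 8.2 does not replace treated patients who leave the trial, outside the safety run-in.
- **Censoring of survival.** Protocol 9.1.1: "Patients who start a new anti-cancer therapy will be censored for survival and progression analyses at date of last scan" before that therapy. Protocol 10.4.2 and SAP 7.1 use last contact: "Subjects who are still alive will be censored on the date of last contact".

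**The concern.** Membership of the set depends on what happens after time zero. Patients who enter through the Week 12 scan were alive at about Week 12 by construction (the imaging window is ±7 days), so deaths before Week 12 inside the set come almost only from early progressors. A patient who dies at Week 4 of infection, toxicity or an unrelated cause is removed. A 12-week survival rate in a group that mostly had to reach Week 12 is hard to interpret, and the later Kaplan-Meier curve inherits the same selection.

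The conflicting rules matter for a different reason. Different readings give a different 15 for the Stage 1 look and a different 30 for the final count, and the Simon rules depend on both.

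**Working it through.** **Plan's own figures first.** Exact two-stage binomial for Protocol 10.2, with early stop = P(X₁ < r₁) and rejection = Σ over x ≥ r₁ of P(X₁ = x)·P(X₂ ≥ r − x):

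| Cohort | Rule | Type I error | Power | Early stop under null |
|---|---|---|---|---|
| A (5% v 18%) | ≥1/15, ≥4/30 | 0.058 (stated 6%) | 0.800 (80%) | 0.463 (46%) |
| B (13.3% v 29%) | ≥2/15, ≥7/30 | 0.092 (9.2%) | 0.801 (80.1%) | 0.388 (38.8%) |

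All reproduce. They concern ORR; no OS figure is stated.

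**Direction of the OS error.** If a share e of treated patients is excluded, S_all = (1 − e)·S_in + e·S_out, so S_in − S_all = e·(S_in − S_out). This is positive exactly when excluded patients survive less well to Week 12. Example: 30 evaluable patients with 3 deaths give 27/30 = 90.0%. Three further treated patients excluded and dead by Week 12 make it 27/33 = 81.8%. If those three were alive it would be 30/33 = 90.9%.

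**Illustrated size.** Medians come from Protocol 3.3 (below 6 and below 12 months for CPI non-responders, used here at their upper limits) and 3.2.1.1 (7.5 months on nivolumab, 12.3 months on pembrolizumab alone with CPS ≥1, nearer Cohort B). Assume exponential survival and 52/12 weeks per month: S₁₂ = 0.5^(12/(m·52/12)). Let f be the share of pre-Week-12 deaths excluded and a the share of treated patients excluded while alive at Week 12. Then S₁₂′ = (S₁₂ − a)/(1 − f(1 − S₁₂) − a). With a = 0:

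| Median (months) | S₁₂ | f = 25% | f = 50% | Excluded per 30 treated |
|---|---|---|---|---|
| 6 | 72.6% | 78.0% | 84.1% | 2–4 |
| 7.5 | 77.4% | 82% | 87.3% | 2–3 |
| 12 | 85.2% | 88.5% | 92.0% | 1–2 |
| 12.3 | 85.6% | 88.8% | 92.2% | 1–2 |

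With a = 5%, the 6-month row becomes 76.7–83.2% and the 12-month row 87.9–91.6%.

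**Reversal.** Setting S₁₂′ = S₁₂ gives a = f·S₁₂. At f = 10% the break-even is 7.3% (6 months) or 8.5% (12 months). With f = 10% and a = 10%, reported OS is 71.8% against 72.6%, and 85.0% against 85.2%.

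**Precision.** The 95% half-width at n = 30 is 1.96·√(S(1 − S)/30): 16.0 points at 72.6% and 12.7 at 85.2%.

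**Futility count.** If the 15 in Cohort A are filled only with non-progressors, as SAP 2.4 can be read, and a share g progresses by Week 12, the null response rate among those counted is 0.05/(1 − g). The chance of 0/15 is then 0.380, 0.329, 0.271 and 0.206 for g = 20, 30, 40 and 50% (assumed), against 0.463.

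**ORR.** The stated type I errors hold if the null rates refer to evaluable patients, which fits the wording of Protocol 5.2 and SAP 2.2. Only if they are all-treated rates, and a share u of treated patients are non-evaluable non-responders, does the rate among evaluable patients become p₀/(1 − u). For u = 5–20%, type I error is then 6.8–11.0% (A) and 11.3–21.6% (B).

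**The case against.** The case on the other side is strongest on size and on the thinner conflicts.

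- **Size.** Nothing in the documents supports excluding 25–50% of early deaths. Most early deaths may follow progression and so stay in the set. Eligibility (life expectancy of at least 3 months, ECOG 0–1, no rapid deterioration on prior therapy) should lower early mortality, and imaging at discontinuation should leave fewer living patients without a scan. Protocol 3.1.2 reports no fatal events among the first 11 patients. Every illustrated shift is smaller than the confidence half-width. This stands as a limit on magnitude. Eleven patients with unstated follow-up do not give an early-death rate, though, and wide intervals do not excuse an avoidable systematic error.
- **Population.** The synopsis says all patients take part in the overall efficacy analysis, and SAP 7.1 ties the set to the primary analysis at Week 12. The synopsis sentence most naturally means both stages together. Protocol 10.4.2 is explicit for all efficacy analyses, and the SAP names no other set for OS.
- **Conflicts.** The SAP 2.4 futility sentence appears in Protocol Appendix C as superseded protocol text, so it is probably a leftover; it is nevertheless live in the SAP. The two sentences in Protocol 10.3 can be read together if clinical progressors need at least one scan. The two replacement rules overlap only in part. These points soften the conflicts but do not resolve them.
- **Visibility.** Patients removed from each set are tabulated (SAP 5), and deaths in the AE reporting period are summarised and listed (SAP 8.3). The exclusions will be partly visible, but neither output gives an all-treated survival curve.

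**Conclusion.** The concern holds. Followed as written, the plan leaves some early deaths out of an endpoint timed from first dose. The 12-week OS rate is too high if excluded patients survive less well to Week 12, which is likely but not certain. The illustrated overstatement is about 5 to 12 points at a 6-month median and 3 to 7 points at a 12-month median. It rests on exponential survival, 25–50% of early deaths excluded and no living patient excluded, none of which the documents establish.

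OS is descriptive and plays no part in the go/no-go decision. The Simon operating characteristics are correct for evaluable-patient rates. Of the rule conflicts, the SAP 2.4 futility sentence has the most practical reach because it changes the Cohort A Stage 1 denominator.

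A separate point: SAP 7.1 censors PFS at the last scan before treatment discontinuation, although the synopsis and Protocol 9.1.1 continue imaging until progression. No size is claimed for that. This should be fixed; it does not invalidate the design.

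**What to change.** 1. Analyse OS and PFS in the Safety Analysis Set. Censor OS at last contact and remove survival from the new-therapy censoring sentence in Protocol 9.1.1. For PFS, state that a death before any scan is an event: SAP 7.1 counts death as an event but also censors patients with no assessment at treatment start.
2. Keep the evaluable-set ORR as primary. Add ORR in all treated patients as a sensitivity analysis, counting no Week 12 assessment as non-response. State which population the null and alternative rates describe.
3. Write one rule for the evaluable set, one for the 15 and the 30, and one for replacement. Reconcile the synopsis, Protocol 10.3 and SAP 4; SAP 2.4 with the synopsis, Protocol 10.5 and SAP 9.5; and Protocol 5.2 and SAP 2.2 and 9.1 with Protocol 8.2.
4. In the SAP's PFS rules, use scans collected after treatment discontinuation.

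The cost is SAP wording and a protocol clarification. The analysis set exists and the data are already collected. Reported OS and ORR may come out somewhat lower. The Simon rules and their power do not change.
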